### Treatment Compliance

Compliance with medications will be assessed at each study visit by direct questioning and study medication count of unused study medication and packaging to be returned at each visit. Study medication dispensing records will be obtained.

### 13. Concomitant Medication

See Attachment B.

### 14. Adverse Events

Adverse events (AEs), especially those for which the relationship to study medication is not "unrelated," will be followed up until they have returned to baseline status or stabilized at the discretion of the

Version: 05.01.17 (Amendment L) Page 23 of 36 principal investigator. If after the follow-up period, return to baseline or stabilization cannot be established an explanation will be recorded in the source documentation.

# 15. Steering Committee and Data Safety Monitoring Board

The **Steering Committee** will serve as the operational governing board for the project. The Steering Committee will monitor and review reports from the Data Safety Monitoring Board (described below) and any serious AEs. It will oversee the conduct of the trial and progress towards meeting study milestones. It will meet following an award notice and quarterly during the conduct of the trial. The Steering Committee will be chaired by the study PI and will include the CTSI Director, senior statistician, senior pharmacologist, Lilly representative *ex officio*, NIH Project Scientist, NIH Program Officer, and two external scientists with expertise in early stage clinical trials and statistics. The **Steering Committee** will be charged with the review of all relevant data at the end of Stage 1 with the purpose of determining if Go/No go criteria has been met. The relevant data include adverse events considered "probably" and "possibly" related to study drug or study procedure, QTcB values, and TT levels.

Steering Committee, Eli Lilly scientists and NIH scientists and program officers determined that the Stage 1 sample size (10 subjects per arm) was too small to draw conclusions about cortical target engagement and efficacy and therefore these related endpoints will not be considered in the Go/No Go decision. The IU Adult Psychiatry **Data Safety Monitoring Board** (DSMB) will be responsible for data and safety monitoring. DSMB is responsible for reviewing study procedures, AEs, safety mailings (if applicable), enrollment, active subject progress, drop-out rates, and ongoing conduct of the research. The DSMB members can ask questions and make comments and/or recommendations to the investigators. The IRB is notified of significant findings by way of the DSMB meeting minutes at the time of continuing review. DSMB members consist of Department of Psychiatry faculty members who are not investigators on this trial. Data on the number of subjects enrolled and the number of AEs will be reviewed by the Board at least quarterly and more frequently if needed. The resulting report will be issued to the IU IRB at least at the time of continuing review or more frequently by request. Any unanticipated events will be immediately directed to the PI who will follow the IRB reporting procedures.

The DSMB will be responsible for reviewing all safety and testosterone data for the first 10 subjects treated with 150 mg/day in Stage 2 to determine if it is safe to further randomize subjects to this dose (as described in Section 12 above).

# 16. Statistical Methods

### Data Management

Data management will be performed by the Indiana CTSI Design and Biostatistics Program under the direction of [name]. The study database will be set up in OnCore clinical trial software system for data acquisition and management, including establishing a trial eCRF, procedures for randomization and biomarker acquisition and tracking. All procedures will conform to FDA GCP requirements. Data will be quality checked and entered into data analytic programs on a continual basis throughout the conduct of the study to be certain analyses of all relevant variables are available on the established timeline for the ADC to make the Go/No go decision at the end of Stage 1.

#### LY500307: Schizophrenia

#### Stage 1 Dose Selection Analyses

**Go/No go criteria: At the end of Stage 1, relevant data will be provided to the Steering Committee** to make the Go/No go decision. Two LY500307 doses (25 mg/day or 75 mg/day) will be evaluated in Stage 1 to determine which dose will be advanced to Stage 2 for continued dose assessment, cortical target engagement and efficacy assessment analyses. Advancement to Stage 2 will be determined according to the following Go/No go criteria: 1) Lack of a safety signal as defined by SAEs, concerning AEs deemed to be probably related to study medication, absolute QTcB of 450 msec or greater or a change from baseline of 60 msec or greater during the active treatment phases, and 2) lack of TT suppression as determined by a decrease in total testosterone plasma concentrations from baseline levels of at least 50% in at least 5 of 10 subjects per LY500307 dosing arm for two of three consecutive post-randomization values. Testosterone suppression reflects ER $\alpha$  engagement and lack of ER $\beta$  selectivity.

It is anticipated that at any given dose there will be variability in the observed individual concentration exposures. The dose-concentration-response analysis will provide additional "points" that will be shared across subjects to assist in defining the nature of the concentration response relationship. This will be particularly important if the relationship has an emax or sigmoid emax shape with multiple parameters to be identified. The four concentration response relationship types will be explored; linear, exponential, emax and sigmoid emax, and the models will be implemented using a linear or nonlinear mixed effects modeling framework in NONMEM VII to facilitate sharing of data across subjects while preserving within-subject correlation.

There will be two tiers to the examination of whether there is a concentration effect related signal. The first "test" is based on the change in the objective function value when a concentration factor is included in the model as either a linear or exponential effect. That is, is there any detectable effect of incorporating the individualized concentration (we will use the area under the curve derived from the Empirical Bayes Estimates of the PK parameters for each subject). An alpha level for significance of 0.05 will be used. If there is a significant difference in the evaluation at test 1, the additional model structures will be

Version: 05.01.17 (Amendment L) Page 25 of 36 evaluated to determine what "shape" appears to best describe the relationship between concentration and response.

As stated above, four concentration response relationship types will be compared (linear, exponential, emax, sigmoid emax). These are standard PD relationships and, in particular, the emax and sigmoid emax models are based on assumptions that derive from receptor occupancy theory and thermodynamic laws similar to the PK model. These models will be constructed and tested utilizing a linear/nonlinear mixed effects modeling approach. Objective function value differences, information criteria (e.g. AIC) and simulation based model performance evaluation techniques such as visual predictive checks will be utilized to evaluate model performance and guide model selection for the concentration effect relationship. Once a model is selected, the responses for a particular dosage can be simulated, incorporating between subject variability as well as parameter uncertainty identified using the modeling approach described above. These simulations will generate a distribution of predicted responses for dosages of interest (including placebo as the zero dose condition). The simulated/predicted responses can be examined to evaluate whether or not there is overlap in the distributions by percentile and provide an answer as to whether or not a particular dosage administered to subjects results in a distinguishable difference in response from placebo. In addition, the model can be used to examine the effect of increasing the numbers of subjects to distinguish drug effect from placebo at any number of dosages under different trial conditions.

Intent-to-Treat Analyses: Point estimates and the corresponding confidence intervals for the primary study endpoints (biomarkers and efficacy measures) at week 8 will be obtained. Statistical tests will be performed based on one-sided test at the 10% level of significance with an adjustment for multiple comparisons for the 3 primary efficacy outcome measures with each primary measure tested at an alpha threshold of p<0.0333 as noted above. One-tailed tests are planned because the main interest of this study is to determine if LY500307 is superior to placebo and thus has produced a sufficient efficacy signal in one or more of the three primary efficacy outcome measures to warrant further assessment in subsequent larger, confirmatory trials. It is therefore a priority of this data analytic plan to avoid a "false negative" (i.e., falsely concluding LY500307 lacks efficacy) that may lead to prematurely terminating further development of the compound.

A "per protocol" analysis will restrict the analysis to subjects who receive minimal exposure to the intervention, have a minimal number of longitudinal evaluations, and/or are free of major protocol violations. A "completer" analysis will only include subjects who completed treatment without exiting or prematurely terminating from their assigned treatment. Because subjects may be removed differentially across the treatment arms in these analyses, both approaches are vulnerable to differential selection bias and will be interpreted cautiously.

Repeated Measures Analyses: Most of the study outcomes are observed repeatedly at well-defined timepoints post-randomization, so the primary analyses are based on mixed models for repeated measurements (MMRM). This includes the mixed effects models for continuous outcomes (normally transformed if necessary) as implemented in PROC MIXED in SAS in which subjects are included as random effects. The fixed-effects predictors include the overall mean, the treatment effect, the time effect, the treatment × time interaction plus selected covariates. Initially, time will be treated as a categorical variable to avoid arbitrary assumptions on the nature of the trend over time. Hypotheses will be tested by deriving contrasts among the model parameters, including between-group differences at the end of study, and the effect size of treatment will be estimated accordingly. This primary analysis will be applied to each of the primary and secondary outcomes.

Covariates in Regression Models: The baseline value of the outcome, centered about its sample mean, will be included in each analysis. The baseline value tends to correlate with post-randomization

Version: 05.01.17 (Amendment L) Page 26 of 36 outcomes, and this maneuver reduces residual variance, thus increasing statistical power and the precision of the estimated treatment effect. Otherwise, only a small number of prognostic factors, e.g. age, found to be imbalanced at baseline, will also be entered into the model.

Missing Data: For this study, missing data falls in to one of two general categories: The first is data that is missing because of missed visits or early termination. The second is related to incomplete data. The former will not affect the results of the mixed-effects model, which is unbiased if missing-at-random assumptions are met; sensitivity analyses will also be performed as described below. The problem of incomplete data in composite measures will be addressed in the case of the cognitive measures by following MATRICS Neurocognition Committee guidelines for imputation (94). For other instruments, total and subscale scores will be imputed using the average of the available items as long as 80% or more of the individual items are available. A low dropout rate is anticipated because subjects will have met a priori clinical stability criteria before randomization and those agents will not be altered throughout the course of the active treatment phase. For drop-outs, sensitivity analyses will as multiple imputations if drop-out is higher than expected.

Other Confounders Arising Post-Randomization: Analyses will be conducted to investigate: (a) adherence to the assigned study medication, (b) co-administration of psychotropic medications, and (c) discontinuation from the study intervention, and logistic regression analysis will be applied to investigate these factors. First, it will determine whether these effects occur differentially across the treatment arms suggesting that a differential selection bias may have influenced the results. Then, whether baseline characteristics are predictive of any behavior will be evaluated. This will include demographic characteristics, initial severity as measured by the baseline values of the outcome variables, and clinical characteristics such as diagnoses and medications taken at baseline. Finally, these confounding factors will be included as covariates in the primary analyses to investigate whether the conclusions on treatment effects are altered.

Pharmacokinetics (PK): These data will be used in post hoc analyses to potentially explain inter-subject variability and toxicity.

#### Brain Imaging Analyses

Quality control, preprocessing and statistical analyses for all scans (see "MRI Methods") will follow established protocols as in our previous publications (e.g., working memory (95-97), episodic memory (98), Resting DMN connectivity (99), PASL perfusion (100), DTI (101, 102), structural MRI (103-105)). Region of interest (ROI) predictions for LY500307 treated vs. placebo effects are as follows: working memory (increase, frontal & parietal), episodic verbal encoding/retrieval (increase, hippocampal & DLPFC) and resting state (increase DMN & hippocampal/DLPFC connectivity). PCASL perfusion may show parallel increases to fMRI (above). DTI white matter tractography and gray matter density/cortical thickness will be examined for possible drug effects such as improvement in GM and WM markers. Additional exploratory analyses will assess whether baseline imaging variables predict treatment response and relationships with cognition and ERP measures (below) will also be evaluated.

#### Event Related Potentials Analyses

The data analytic plan for the three ERP measures (P300, MMN, and ASSR ERSP) will follow the repeated measures approach outlined above for other secondary variables and described in our previous protocols (7, 8, 92). Each variable is listed with the predicted effect on the LY500307 treated compared to the placebo treated control group: P300 amplitude (increased), P300 latency (decreased), MMN amplitude (increased), ASSR ERSP power (increased). In exploratory analyses, it will be tested whether

Version: 05.01.17 (Amendment L) Page 27 of 36 baseline ERP values predict response on the primary and secondary clinical outcome measures in the treated groups.

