NIMH Research Domain Criteria (RDoC) Initiative: The NIMH RDoC initiative, which is a component of the NIMH strategic plan, encourages the assessment of dimensions of observable behaviors and brain functions that may cut across traditional diagnostic categories (see NIMH/RDoC web page). RDoC principles have informed multiple aspects of the study design. While the DSM diagnosis of schizophrenia will be used for entry into the protocol, this heterogeneous disorder will also be characterized by dimensional measures of symptoms, cognitive processes and neurobiological function. This will enable the evaluation in secondary analyses whether these dimensional measures predict treatment response. Second, working memory and episodic memory outcomes will be evaluated across units of analysis, including behavioral, fMRI and ERPs. Three working memory paradigms recommended by the RDoC Working Memory Workshop were selected: N-back (which is coupled with fMRI), Letter Number Sequencing and Spatial Span. The ERP paradigms, P300 and MMN, both exemplify the construct of "Change Detection Tasks." Thus, the findings from this study will likely assist in the validation of the sensitivity of several key RDoC constructs to estrogen modulation across multiple levels of analysis.

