### Sample Size Determination

Thirty subjects will be randomly assigned to three arms (1:1:1) in Stage 1. In Stage 2, 70 additional subjects will be randomized to placebo, the selected LY500307 arm from Stage 1, or the 150 mg/day arm. Thus a total of 100 subjects will be randomized for the study. In a study of chronic schizophrenia,

Version: 05.01.17 (Amendment L) Page 14 of 36 Shekhar et al (52) reported significant effects of the mixed M1/M4 agonist xanomeline (N=20) on verbal and working memory (p < 0.05) and trend effects of negative symptoms (p = 0.08) with effect sizes up to 0.9(52). Based on the estimates from a cross-over study of a nicotinic agonist in patients with schizophrenia (53), it is reasonable to expect an improvement in the working memory score with a mean of 4.5 and a standard deviation of 7.3 using data from the less effective of two doses in that study. Thus for this study, we assume a treatment effect size of 0.61 between the placebo group and the LY500307 treated group. The power estimate based on the variance of the change is conservative for the proposed analyses that actually use baseline outcome values as covariates. We will test the treatment effects on the three primary efficacy measures (negative symptoms, working memory and verbal episodic memory) at the end of Stage 2 with one-tailed tests at an overall alpha=0.1 (see Stage 2 Efficacy Analysis in Section 16.0). Adjusting for multiple comparisons, the test for each of the three individual efficacy outcomes will be performed at alpha=0.0333. The fMRI data will be tested at alpha=0.05. With 30 subjects each in the placebo, 75mg and 150 mg groups across the entire study, 10 subjects assigned to 25 mg/day from Stage 1, and the employment of the dose-concentration-response analytic strategy, we will have >80% power to detect a beneficial treatment effect on each outcome for any effect size >0.61 (measured in SD of the change).

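### The exploratory test of baseline ERP values as predictors of response uses the treated groups only, so it cannot tell a prognostic marker from one that predicts response to LY500307

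*Combined protocol and SAP*

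**What the plan says.** Section 16 (Statistical Methods) has two passages on baseline predictors, and Section 4 has one.

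- **Event Related Potentials Analyses.** Four ERP variables are listed: P300 amplitude, P300 latency, MMN amplitude and ASSR ERSP power. The predictor sentence opens "In exploratory analyses, it will be tested whether" and goes on "baseline ERP values predict response on the primary and secondary clinical outcome measures in the treated groups". It names no comparison with placebo, no interaction term and no significance level.
- **Brain Imaging Analyses.** "Additional exploratory analyses will assess whether baseline imaging variables predict treatment response". No restriction to treated subjects is stated, and no interaction test either.
- **Rationale for Primary Endpoints, RDoC paragraph.** On dimensional measures of symptoms, cognition and neurobiology in general: "This will enable the evaluation in secondary analyses whether these dimensional measures predict treatment response". Again there is no treated-only restriction.

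The repeated-measures model in Section 16 has treatment, time, their interaction and selected covariates. The covariate paragraph adds the baseline value of the outcome to each analysis. Neither contains a baseline-ERP term or its interaction with treatment.

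**The concern.** Predicting response to a drug means that the effect of drug against placebo differs across values of the marker. A slope of outcome on baseline ERP among treated men alone does not estimate that. It mixes any drug-specific association with any association that would be present without the drug. A larger treated-only sample does not help, because it makes a purely prognostic slope more likely to reach significance.

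The protocol's own text makes a prognostic link plausible, though it does not establish one. The ERP Methods section says that MMN amplitude has been correlated with psychosocial function and that P300 indexes working memory. Functioning scales are among the secondary outcomes, and working memory is a primary outcome. What is at stake is how the exploratory result is interpreted: a general marker of course could be taken for a marker of benefit from LY500307.

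**Working it through.** **The plan's own figure.** There is none for the predictor analyses. The only stated power (above 80%) concerns the primary efficacy comparison and is not an input here.

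**Inputs from the documents.** Sample Size Determination gives 30 placebo, 10 at 25 mg/day, 30 at 75 mg/day and 30 at 150 mg/day. That is 10 + 30 + 30 = 70 treated and 30 placebo.

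**Assumptions.** Two-sided 0.05 level; treated arms pooled; complete data; no drug effect. The prognostic correlation r between baseline ERP and outcome is the same in every arm and is taken after allowing for the baseline outcome. No document gives r, so 0.1 to 0.3 is shown as a range.

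**Step 1: the treated-only test.** Fisher's approximation gives d = atanh(r) × √(n − 3), with rejection probability Φ(d − 1.96) + Φ(−d − 1.96). For n = 70, √67 = 8.185.

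| r | d | Formula | Simulation (20,000 trials) |
|---|---|---|---|
| 0.1 | 0.821 | 13.0% | 13% |
| 0.2 | 1.659 | 38.2% | 39% |
| 0.3 | 2.533 | 71.7% | 72% |

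At r = 0 the simulated rate is 5%.

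**Step 2: the interaction test.** The slope in the 70 treated men is compared with the slope in the 30 placebo men, using a pooled residual variance. Both slopes are equal by construction, so the correct rejection rate is 5%. Simulation gives 5.3%, 4.9% and 5.1% at r = 0.1, 0.2 and 0.3.

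**Step 3: arms tested separately.** The wording does not say whether treated arms are pooled. For one arm of 30, √27 = 5.196, so d = 0.521, 1.053 and 1.608, and the rejection rates are about 8%, 18% and 36%. The excess is smaller but does not disappear.

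**Step 4: link only through the baseline outcome.** Suppose baseline ERP correlates 0.3 with the baseline outcome, the baseline outcome correlates 0.7 with week 8 (both assumed), and ERP has no other path to week 8. With the baseline outcome in the model, the treated-only test rejects in about 5% of simulated trials. The inflation therefore needs an association beyond the baseline outcome.

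**Step 5: price of the interaction test.** With ERP and residual outcome in SD units, the treated-only slope has standard error √(1/70) = 0.1195. The slope difference has √(1/70 + 1/30) = 0.2182. The ratio is 0.2182 / 0.1195 = 1.83. The slope difference detectable with 80% power is (1.960 + 0.842) × 0.2182 = 0.61 SD of outcome per SD of ERP. This 0.61 matches the plan's assumed effect size only by coincidence.

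**The case against.** The strongest reply is that the sentence is declared exploratory and itself limits its claim to treated subjects. No primary aim or Go/No go criterion uses a baseline predictor, and further development is tied to superiority over placebo on the primary efficacy outcomes. The size rests on correlations that no document supplies. The planned adjustment for the baseline outcome would also remove much of any prognostic link and of regression to the mean, and alternate test forms limit practice effects. All of this stands, and it keeps the point minor. It does not remove the point: the label lowers the weight of the result but does not change what the test estimates.

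A reader might infer four stronger claims that the documents do not support:

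- **That all baseline predictors are tested in treated subjects only.** The restriction is explicit for ERP alone. The imaging and RDoC passages do not state it.
- **That a prognostic marker would be reported as a predictor of drug response and used to select patients later.** The plan has no such reporting rule and describes no such use.
- **That the lack of multiplicity control is a defect.** The only stated correction is "with an adjustment for multiple comparisons for the 3 primary efficacy outcome measures". Leaving tests uncorrected is acceptable when they are declared exploratory, and adding a formal correction is a matter of preference.
- **That the RDoC paragraph contradicts Section 16** because it says secondary where Section 16 says exploratory. That paragraph covers a wider set of measures, and the difference is loose wording.

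**Conclusion.** The point holds for the baseline ERP predictors, as a minor matter that is cheap to improve. As written, the analysis cannot separate an ERP value that is prognostic in every arm from one that modifies the effect of LY500307. If such a prognostic link exists beyond the baseline outcome, the pooled treated-only test finds it significant in about 13% to 72% of trials for assumed correlations of 0.1 to 0.3, even when the drug does nothing. The interaction test holds about 5%. If there is no such residual link, there is no inflation. The wording that can be supported is that a marker could be misread, not that it will be. The figures rest on the assumed correlations, an assumed two-sided 0.05 level, pooled treated arms and complete data.

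**What to change.** In Event Related Potentials Analyses, replace the treated-only test with a test of the baseline-ERP-by-treatment interaction in all randomised subjects. Use the planned MMRM with the baseline outcome as covariate, and take LY500307 (doses pooled) against placebo as the contrast. Report the estimated slope with its confidence interval in each arm, placebo included. State the same approach for the predictors in Brain Imaging Analyses, where the population and model are now left open. Keep the results labelled exploratory and hypothesis-generating.

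The cost is wording only. Attachment A schedules baseline ERP, baseline MRI and the clinical outcomes without distinction by arm, so the placebo data will exist. The loss is precision: the standard error is about 1.8 times larger, with 80% power only for a slope difference near 0.61 SD per SD. Few predictors will be declared, and a non-significant interaction should not be read as evidence that none exists.
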